9.2.1. Sample Size Sensitivity

Considering the variability of AUC(0-3h) and Cp10, Table 6 shows the scenarios for different sample size and the precision estimates for IH vs. IM in Group 1.

Table 6 Estimated 90% Confidence Intervals for Treatment Ratios for Sample Size Sensitivity

%CVb	N	Precision	Assuming ratio 1, the confidence interval
44.35%	5	61.90%	(0.61, 1.61)
	15	29.80%	(0.77, 1.29)
65.96%	5	98.00%	(0.50, 1.98)
	15	44.80%	(0.69, 1.44)
	20	37.40%	(0.72, 1.37)
85.35%*	5	131.90%	(0.43, 2.31)
	10	75.90%	(0.56, 1.75)
	15	57.60%	(0.63, 1.57)
	20	48.00%	(0.67, 1.48)

* 85.35% was the largest between subject CV for AUC(0-10) observed for FTIH study 201558 [GlaxoSmithKline Document Number: 2016N277949_00]

9.2.2. Sample Size Re-estimation or Adjustment

No formal sample size re-estimation is planned for this study. However, if the variability is high (for example approaching 85%) then the sample size for Group 1 may be increased to a maximum of 10 additional subjects per treatment arm (IH and IM only).

9.3. Data Analysis Considerations

9.3.1. Analysis Populations

Enrolled Population	
 Defined as all subjects who were enrolled for the trial irrespective of whether they were randomized or not and for whom a record exist on the study database. This population will be used for summarizing screening failure reasons.
All Subjects Population	
 Comprise of subjects who receive at least one dose of study medication. This population will be used for the study population and safety displays.
Pharmacokinetic Population	
 Subjects in the 'All Subjects' population for whom a pharmacokinetic sample was obtained and analysed. PK population will be the population for reporting PK data.

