2.2.2. PK Specimen Stability as Observed in 205920

Prior to the initiation of the current trial, a sample-handling process was developed using blood from pregnant subjects of at least 37 weeks gestation to ensure ex-vivo oxytocin stability in specimens collected from Group 1 TSL subjects.

Per protocol, after 10 subjects had completed all procedures in Group 1, an informal interim PK analysis was conducted. It was observed that in the majority of the plasma samples collected from TSL subjects, oxytocin concentrations were below the limit of quantification (BLQ) or at very low concentrations (approximately 3pg/mL) approaching

the lower limit of quantification (LLQ) of the assay (2pg/mL). This was seen across both IM and IH routes of administration. This was an unexpected finding which has been confirmed by re-analysis of selected samples. As such, it is considered that it may be due to ex-vivo oxytocin instability related to uninhibited oxytocinase and peptidases, which are believed to be at increased concentrations in the plasma of postpartum women compared with non-pregnant women, and women at 37 weeks gestation. This finding resulted in a temporary halt to the trial.

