4.3. Type and Number of Subjects

Sufficient subjects will be screened such that approximately 20 subjects complete all study procedures in Group 1, and approximately 10 subjects complete all study procedures in Group 2 (approximately 5 in each cohort of Group 2). Refer to Section 6.3 for treatment assignment information.

If subjects prematurely discontinue the study, additional replacement subjects may be recruited and assigned to the same treatment at the discretion of the Sponsor. Replacement subjects will complete all study procedures as outlined in Section 7.1.

If the PK variability between subjects in Group 1 is higher than expected, it may be required to increase the sample size up to a maximum of 10 additional subjects per treatment group for IH and IM. In the event of this, sufficient subjects will be screened such that a maximum of 50 subjects complete Group 1.

If a dose adjustment is required in either group, additional subjects may be recruited such that a full 10 subjects receive the final IH or IV dose. See Section 6.4.1 for more details.

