7.4. Pharmacokinetics

7.4.1. Blood Sample Collection

Blood samples for pharmacokinetic (PK) analysis of oxytocin will be collected at the time points indicated in Section 7.1, Time and Events Table. The actual date and time of each blood sample collection will be recorded. The timing of PK samples may be altered and/or PK samples may be obtained at additional time points to ensure thorough PK monitoring.

At each time point, 4 mL of blood will be collected into study-specific tubes formulated to further inhibit peptidase activity. Additional details regarding collection/shipping procedures are provided in the SRM.

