9.2. Sample Size Considerations

A sufficient number of subjects will be enrolled to ensure approximately 20 evaluable subjects (10 in each of the IM and IH groups) complete all dosing and critical assessments in Group 1, as well as 5 subjects in each cohort in Group 2. Whilst sample size is based on feasibility, precision calculation was also done to approximate the estimate of the expected half width of 90% CI around point estimate for the main comparison of interest (IH oxytocin to 10 I.U. IM oxytocin in women in TSL) using a t-test.

Table 5 illustrates the associated 90% CIs for the mean treatment ratios, assuming between subject SDs of 0.424 and 0.601 (SDs are based on log transformed data) for AUC (0-3h) and Cp10 respectively, for the comparisons of interest detailed in Section 9.1. Calculations are based on a symmetric two-tailed procedure on the loge scale and a type I error rate of 10%. These values represent estimates of the between-subject variability observed in the FTIH study 201558 [GlaxoSmithKline Document Number 2016N277949_00].

Table 5 Estimated 90% Confidence Intervals for Treatment Ratios

N	Parameter	Between Subject Standard Deviation (SD)	Estimated Treatment Ratio	Precision	Expected 90% CI
10	AUC(0-3h)	0.424 (CVb=44.35%)	1	38.30%	(0.72, 1.38)
10	Cp10	0.601 (Cvb=65.96%)	1	58.20%	(0.63,1.58)

The precision estimates are deemed acceptable to assess the study objectives at this stage of development.

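### The PK Population still includes the 10 Group 1 women sampled before the halt, so if their samples did degrade, the pooled third-stage-of-labour profile is biased low and the IH/IM interval is widened.

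*Protocol*

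**What the plan says.** Section 9.3.1 defines the PK Population as subjects in the All Subjects "population for whom a pharmacokinetic sample was obtained and analysed", and adds: "PK population will be the population for reporting PK data". It sets no condition on tube type, sample integrity or time of sampling relative to the halt.

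Section 2.2.2 reports: "Per protocol, after 10 subjects had completed all procedures in Group 1, an informal interim PK analysis was conducted". In most of the plasma samples "oxytocin concentrations were below the limit of quantification (BLQ) or at very low concentrations (approximately 3pg/mL) approaching" the assay's lower limit of 2 pg/mL, on both routes. Re-analysis of selected samples confirmed this. The protocol gives ex-vivo instability as a possible cause, and the trial was temporarily halted. Section 7.4.1 now states that "4 mL of blood will be collected into study-specific tubes formulated to further inhibit peptidase activity".

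Section 9.4.2.1 compares IH with IM on log-transformed parameters, with treatment as a fixed effect and subject as a random effect, and no term for sampling procedure. Section 9.2 plans "approximately 20 evaluable subjects (10 in each of the IM and IH groups"). Section 4.3 provides replacements only for women who discontinue early.

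**The concern.** The 10 pre-halt women were dosed, and their samples were obtained and analysed, so they meet the definition. No current section removes them, analyses them apart or replaces them; they completed, so the replacement rule does not reach them. Amendments 02 and 03 were both written after the problem was known and revised the neighbouring Section 9.3.2, but left 9.3.1 as it was.

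The primary Group 1 objective is to characterise the PK in the third stage of labour. Under the stated rule, a substantial share of each arm's summary could reflect sample handling rather than pharmacokinetics, and the same women enter the IH vs IM comparison.

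**Working it through.** **1. Reproduce the plan's figure.** Inputs from Section 9.2: log SD 0.424 for AUC(0-3h) and 0.601 for Cp10, 10 women per arm, two-sided 90% CI. The expected half-width on the log scale is h = t(0.95, 2n−2) × c4 × SD × √(2/n), where c4 is the expected value of the sample SD divided by the true SD. For n = 10, t × c4 = 1.734 × 0.986 = 1.710.
- AUC(0-3h): h = 1.710 × 0.424 × 0.4472 = 0.324, giving 38.3% and (0.72, 1.38). Table 5 states 38.30% and (0.72, 1.38).
- Cp10: h = 1.710 × 0.601 × 0.4472 = 0.460, giving 58.4% and (0.63, 1.58). Table 5 states 58.20% and (0.63, 1.58).

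The plan's method is recovered.

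**2. Assumptions for pooling.** The protocol gives neither the valid Cp10 level in these women nor the arm split of the 10. I assume:
- 5 pre-halt women per arm (Section 9.3.2.1 plans the review after 5 on each treatment);
- pre-halt Cp10 centred at 3 pg/mL with log SD 0.601;
- valid Cp10 geometric mean M of 10 or 30 pg/mL with the same log SD.

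**3. Case A: the 10 count toward the 20, so 5 + 5 per arm.** Let D = ln(M/3).
- Pooled geometric mean / truth = √(3/M): √0.3 = 0.55 for M = 10; √0.1 = 0.32 for M = 30.
- Pooled SD = √(0.601² + (10/9)(D/2)²). M = 10: D = 1.204, √(0.361 + 0.403) = 0.874. M = 30: D = 2.303, √(0.361 + 1.473) = 1.354.
- 90% CI at ratio 1: h = 1.710 × 0.4472 × 0.874 = 0.668, giving (0.51, 1.95); and 1.710 × 0.4472 × 1.354 = 1.036, giving (0.35, 2.82).
- An SD of 0.874 is a CV of √(exp(0.764) − 1) = 107%. If variability were judged on this set, it would exceed the 85% that Section 9.2.2 gives as its example for adding up to 10 women per arm.

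**4. Case B: the 10 do not count, so 5 + 10 per arm.** The geometric mean factor is (3/M)^(1/3), i.e. 0.67 or 0.46. Pooled SD = √(0.601² + (5 × 10/15)D²/14) = 0.840 or 1.274. With t × c4 = 1.686 and √(2/15) = 0.365, the CI is (0.60, 1.68) or (0.46, 2.19). The 10 post-restart women per arm alone would give (0.63, 1.58).

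Pooling therefore biases the profile under either reading of the target. It buys little or no precision: in Case A, the 5 valid women per arm alone give (0.50, 1.98) for Cp10 (Table 6).

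**5. Effect on the IH/IM ratio.** If pre-halt values sit at the same floor in both arms, the Case A pooled ratio is the square root of the true ratio: 0.60 → 0.77, 1.10 → 1.05, 1.65 → 1.28. A simulation used 5 + 5 per arm, LLQ 2 pg/mL, SD 0.601, an assumed valid IM Cp10 of 20 or 50 pg/mL, and a loss that made about 87–88% of pre-halt IM values BLQ. BLQ values were either set to half the LLQ or treated as missing. A true 0.60 read 0.71 to 0.76; a true 1.65 read 0.95 to 1.49; a true 1.10 read 1.02 to 1.07. With all pre-halt IM values BLQ and treated as missing, the readings were close to truth (0.61, 1.10 and 1.55).

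**The case against.** The strongest reply is that a population for reporting PK data is not an instruction to put all its members into one mean profile. Section 9.4.2.1 sends further detail to the RAP, which is not at hand; Section 9.2 speaks of evaluable women; and parameters are derived and compared only as data permit. Ex-vivo loss is also not proven. Sections 2.1 and 4.5 raise increased clearance in pregnancy as a real possibility, and the in-stream analysis (9.3.2.2) with the halt rule (5.4.6) is there to test the new procedure.

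Part of this stands. Degradation is suspected only, every magnitude above rests on assumed concentrations, and the ratio bias is conditional. It vanishes at a true ratio of 1, or if loss is proportional and balanced with all values quantifiable, and it is small near 1.10, the Cp10 ratio reported from the first-in-human study.

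The rest does not remove the point. The protocol itself fixes the population, the term evaluable is not tied to it, and a later RAP exclusion would depart from the protocol after those data had been seen.

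Three stronger readings are tempting but unsupported:
- **Pooling would carry the ratio across a Table 3 boundary.** Section 6.4.1 uses a ratio of medians at n = 5, and Section 9.3.2.1 repeats that review after restart, so a geometric-mean result on 5 + 5 women does not apply.
- **The statement that "sufficient subjects will be screened such that a maximum of 50 subjects complete Group 1" shows the 10 were to be discarded.** 20 + 2 × 10 = 40, and the other 10 could equally be the 600 mcg women of Section 6.4.1.
- **The Group 1 vs Group 2 comparison is confounded by tube type.** The protocol does not say when Group 2 was sampled or that its samples degraded.

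**Conclusion.** The point holds in conditional form. As written, the analysis set mixes two sampling procedures, one of them suspected of failing, and the model does not separate them. If the suspected degradation is real, the pooled profile is biased downward and the log SD inflated. With 5 + 5 per arm and the assumptions above, the geometric mean is 0.55 to 0.32 of truth and the Cp10 interval is (0.51, 1.95) to (0.35, 2.82) instead of (0.63, 1.58). With 5 + 10 per arm the distortion is smaller but still present. The IH/IM ratio may be pulled toward 1; the documents do not allow a flat statement that it will be. No formal hypothesis is tested, so what is at risk is the descriptive estimate that is the study's primary aim.

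**What to change.** Define the Group 1 set for the main PK summaries and the IH vs IM comparison as women sampled under the revised, post-restart procedure. Present the 10 pre-halt women separately, in a listing or a sensitivity analysis, and keep them in the safety population. The sensitivity analysis keeps their data in view should the in-stream results point away from ex-vivo loss.

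State whether the 10 + 10 evaluable target counts from restart. If it does, Table 5 stands and the change is wording only. If it does not, and 5 post-restart women per arm remain, restate the expected precision from Table 6: (0.61, 1.61) for AUC(0-3h) and (0.50, 1.98) for Cp10. Restoring the Table 5 precision would then take 5 more women per arm, 10 in all. The sponsor should make that choice explicitly, before the post-restart data accrue.

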9.3.2. Interim Analyses

No formal interim analyses are planned. PK data will be reviewed per Section 9.3.2.1, Section 9.3.2.2 and Section 9.3.2.3, and may be shared with any relevant third party to allow for discussion around future partnering opportunities for IH oxytocin.

9.3.2.1. Informal Interim Reviews

PK samples will be analysed and preliminary PK parameters derived following completion of 5 women on each of the following treatments: 400 mcg IH and 10 I.U. IM to women in TSL (Group 1) and 400 mcg IH to non-pregnant women on the combined oral contraceptive (Group 2 Cohort A). Based on the PK profiles the dose of IH oxytocin to be administered to women in TSL will either remain at 400 mcg or be increased (to 600 mcg) (See Section 6.4.1). This decision will be made by the study team in collaboration with the Principal Investigator.

This will be repeated after restart from the temporary halt for Group 1.

9.3.2.2. In-Stream Analysis of Group 1

Following restart from temporary halt, PK specimens from each of up to 5 subjects in Group 1 will be analysed as soon as possible after collection. This will allow for confirmation that the revised specimen collection procedures allow for detection of adequate oxytocin PK profile.

9.3.2.3. Analysis of Group 2

An analysis of Group 2 (non-pregnant volunteers) will be performed once Group 2 has completed to allow for full reporting of non-pregnant volunteer data prior to completion of Group 1.

There will be no changes to the study design or Group 1 of the study as a result of this analysis. The Reporting and Analysis Plan (RAP) will describe the planned analysis in greater detail.

9.4. Key Elements of Analysis Plan

9.4.1. Primary Analyses

9.4.1.1. Safety Analysis

Safety data will be presented in tabular and/or graphical format and summarized descriptively according to GSK's Integrated Data Standards Library (IDSL) standards.

9.4.1.2. Pharmacokinetic Analysis

Pharmacokinetics analysis will be the responsibility of the Clinical Pharmacokinetics Modeling & Simulation department within GlaxoSmithKline. Plasma oxytocin concentration-time data will be analyzed by non-compartmental methods with WinNonlin V6.3 or greater. Calculations will be based on the actual sampling times recorded during the study.

From the plasma concentration-time data, the following pharmacokinetic parameters will be determined, as data permit: maximum observed plasma concentration (C_{max}), time to C_{max} (t_{max}), area under the plasma concentration-time curve [AUC(0-3h) and AUC(0- ∞)], the last observed quantifiable concentration (C_{last}), time of the last quantifiable

concentration (tlast), Cp10, Cp20, Cp30 (observed plasma concentrations at 10, 20 and 30 minutes post-dose, respectively), plasma clearance (CL; IV only), volume of distribution (V; IV only) and apparent terminal phase half-life (t1/2). Other PK parameters may also be determined.

Pharmacokinetic data will be presented in graphical and/or tabular form and will be summarized descriptively. All pharmacokinetic data will be stored in the Archives, GlaxoSmithKline Pharmaceuticals, R&D.

If appropriate, a population PK analysis may also be conducted, in addition the oxytocin plasma concentration-time data may be merged with historical data and analysed as part of a population PK meta-analysis.

9.4.2. Secondary Analyses

Statistical analyses of the PK parameter data will be performed by, or under direct auspices of Clinical Statistics, QSci.

9.4.2.1. Pharmacokinetic Analysis

For evaluating pharmacokinetic treatment comparisons within Group 1 IH vs. IM, point estimates and corresponding two-sided 90% confidence intervals will be computed using a mixed effect model. Loge-transformed PK parameters will be analysed using the model with a fixed effect term for treatment and a random effect term for subject.

Further details of analysis and reporting of PK data will be given in the RAP.

9.4.3. Exploratory Analyses

9.4.3.1. Pharmacokinetic Analysis

For evaluating pharmacokinetic treatment comparisons between Group 1 and Group 2 (IH oxytocin comparison in TSL vs. non-pregnant women on the combined oral contraceptive), and within Group 2 between Cohorts A and B (IH and IV oxytocin comparison in non-pregnant women in the presence and absence of oral contraceptive), point estimates and corresponding two-sided 90% confidence intervals will be computed using a mixed effect model. Loge-transformed PK parameters will be analysed using the model with a fixed effect term for treatment and a random effect term for subject.

Further details of analysis and reporting of PK data will be given in the RAP.

9.4.3.2. Device Acceptability Questionnaire

In Group 1, subject satisfaction with device, including instructions and ease of use, will be assessed. The questionnaire is located in Section [12.7](#)

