3. OBJECTIVES AND ENDPOINTS

3.1. Group 1: Women in TSL

Objectives	Endpoints
Primary	

 To characterize the pharmacokinetics of single doses of IH oxytocin and 10 I.U. IM oxytocin in women in TSL. 	
 Plasma concentration time profile for IH oxytocin and 10 I.U. IM oxytocin. PK parameters: Maximum observed plasma concentration (C_{max}), Observed plasma concentrations at 10 minutes (min) post-dose (C_{p10}), Observed plasma concentrations at 20 min post-dose (C_{p20}), Observed plasma concentrations at 30 min post-dose (C_{p30}), Time to C_{max} (t_{max}), Area under concentration-time curve (AUC), and Terminal phase half-life (t_{1/2}) will be calculated as data permit.
Secondary	

 To evaluate the safety and tolerability of inhaled oxytocin. 	
 General safety parameters: adverse events; absolute values and changes over time of vital signs (blood pressure, heart rate, respiratory rate, temperature).

 To compare pharmacokinetics of IH oxytocin to 10 I.U. IM oxytocin in women in TSL. 	
 C_{max}, C_{p10}, C_{p20}, C_{p30}, Area under the concentration-time curve from time zero (pre-dose) to three hours (h) (AUC[0-3h]) will be compared as data permit.
Exploratory	

 Pharmacodynamic effect of IH oxytocin and 10 I.U. IM in women in TSL. 	
 Pre and post-delivery haemoglobin.

 Participant feedback regarding ease of use, instructions, and perceived ability of patients to use the ROTHALER. 	
 Questionnaire results from participants.

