6.7. Preparation/Handling/Storage/Accountability

- The investigator/designee will be trained to load the ROTACAPS powder capsule into the device, prime the dose and instruct the subjects to inhale from the ROTAHALER inhaler in the appropriate manner. The investigator/designee will always load and prime the ROTACAPS powder capsule in the device before the subject self-administers an IH oxytocin dose
- All subjects will be taught by the investigator/designee to use the device in the “full-tilt” position and to use a “fast and deep” inspiration technique per inhalation, to achieve two rapidly consecutive maximal inhalations for IH oxytocin administration. This will ensure optimal and consistent treatment delivery. For subjects, the training session will be at any time during the 28-day Screening Period, as deemed appropriate by the investigator/designee.
- ROTACAPS powder capsules should be kept in their sealed packaging at room temperature (15-25°C Centigrade [C]). The packaging should only be opened immediately prior to use.
- ROTAHALER inhaler devices will be supplied in bulk and unlabelled to the site. After dosing all ROTAHALER inhaler devices will be uniquely labelled and retained after each dosing session. The devices (which should not be opened up at

the clinical study site) will be stored until further instruction from the sponsor is received.

- The investigator or designee must confirm appropriate temperature conditions have been maintained during transit for all study treatment received and any discrepancies are reported and resolved before use of the study treatment.
- Only subjects enrolled in the study may receive study treatment and only authorized site staff may supply or administer study treatment. All study treatments must be stored in a secure environmentally controlled and monitored (manual or automated) area in accordance with the labelled storage conditions with access limited to the investigator and authorized site staff.
- The investigator, institution, or the head of the medical institution (where applicable) is responsible for study treatment accountability, reconciliation, and record maintenance (i.e. receipt, reconciliation and final disposition records).
- Further guidance and information for final disposition of unused study treatment are provided in the SRM.

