12.7. Appendix 7: Device Acceptability Questionnaire

Device Acceptability Questionnaire

Please answer the following questions regarding your use of the ROTAHALER inhaler for oxytocin.

1. Did you feel confident you had received the medicine?

Yes No Neutral Decline to answer

2. Did you find the inhaler easy to use?

Yes No Neutral Decline to answer

3. Did you prefer to have your medicine from an inhaler instead of an injection?

Yes No Neutral Decline to answer

4. Do you feel using this inhaler is an acceptable way to administer the medicine?

Yes No Neutral Decline to answer

Thank you for answering these questions.

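### The device questionnaire has no item on the instructions and none directly on perceived ability to use the inhaler, although the Group 1 exploratory objective promises both

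*Protocol*

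**What the plan says.** Section 3.1 of the protocol gives this exploratory objective for Group 1: "Participant feedback regarding ease of use, instructions, and perceived ability of patients to use the ROTHALER". The synopsis carries the same objective. The endpoint set against it is "Questionnaire results from participants", and no other data source is named.

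Section 9.4.3.2 says of Group 1 that "subject satisfaction with device, including instructions and ease of use, will be assessed" and points to Section 12.7 (Appendix 7) for the form. It does not mention perceived ability.

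Appendix 7 prints the form in full. Its four items are:

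1. "Did you feel confident you had received the medicine"
2. "Did you find the inhaler easy to use"
3. "Did you prefer to have your medicine from an inhaler instead of an injection"
4. "Do you feel using this inhaler is an acceptable way to administer the medicine"

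Each is answered Yes, No, Neutral or Decline to answer. There is no free-text field. The Time and Events tables in Sections 7.1.1 and 7.1.2 restrict the form to women randomised to inhaled oxytocin.

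**The concern.** The objective names three things to be learned from participants, and the protocol gives one instrument for learning them. When objective and instrument are read together, the instrument does not cover the objective. The instructions appear in both the objective and the analysis section, yet no item asks about them. Perceived ability appears in the objective, yet no item asks whether the woman felt able to use the device.

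This cannot be left to an analysis plan. Such a plan can choose how to tabulate answers, but it cannot supply answers to questions that were never put. If the protocol is followed exactly, the study report must either say nothing on the instructions or infer something about them from items on other subjects.

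**Working it through.** No arithmetic beyond counting applies. The check is a mapping of the four items to the constructs named in the text.

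**Constructs promised**
- Synopsis and Section 3.1: ease of use, instructions, perceived ability (three).
- Section 9.4.3.2: instructions, ease of use (two).

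**Items available in Appendix 7**

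| Item | Content | Construct named in the objective that it measures |
|---|---|---|
| 1 | Confidence that the medicine was received | None directly; at most an indirect sign of perceived ability |
| 2 | Ease of use | Ease of use directly; at most an indirect sign of perceived ability |
| 3 | Preference for inhaler over injection | None |
| 4 | Acceptability of the route | None |

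**Count by construct**
- Ease of use: 1 item.
- Instructions: 0 items, and no proxy among the four.
- Perceived ability: 0 direct items, 2 possible indirect ones.

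So 1 of the 3 constructs in the objective has a direct item, and 1 of the 2 in Section 9.4.3.2.

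**Could the gap be an artefact or a superseded text?** No. The items are numbered 1 to 4, the form closes with a line of thanks, and the same four items appear in every protocol version supplied, from the original through the third amendment.

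**Could the instructions be rated at all?** Yes. Sections 4.1.4 and 6.7 have staff teach every subject the inhalation technique, so the women who answer the form have received instructions on which they could comment.

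**How many women are affected?** Table 2 in Section 6.3 plans 10 women on inhaled oxytocin in Group 1. Section 9.2.2 allows up to 10 more per arm, giving 10 + 10 = 20, and Section 6.4.1 allows for 10 at a second inhaled dose level. About 10 is therefore the base case, not a ceiling.

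**The case against.** The best defence is that perceived ability is not wholly unmeasured. Items 1 and 2 are self-reports by women who have just used the inhaler. A woman who found it easy and was confident that she received the medicine has said something about her ability to use it. This stands in part: it is why the ability gap is stated as the absence of a direct item. It does nothing for the instructions, which neither item mentions.

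A second defence is that the endpoint is exploratory, with no hypothesis, decision rule or sample-size basis attached. That is correct and limits the importance of the point, but the text and the form still disagree.

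Three stronger readings may tempt a reader, and the protocol does not support them:

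- **That the form yields no data on ability.** The indirect bearing of items 1 and 2 makes this too strong.
- **That the ease-of-use item is undermined because staff prepare the device.** Section 6.7 does say "The investigator/designee will always load and prime the ROTACAPS powder capsule in the device". But inhaling is the woman's task in this study, and item 2 rates what she did. Self-administration without trained staff is product background in Section 2; no section plans a conclusion about it from this form.
- **That item 3 is defective because respondents had no study injection.** Preference is in neither the objective nor Section 9.4.3.2, and no comparison of preference between arms is planned.

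**Conclusion.** The point holds in a limited form. The instructions part of the Group 1 exploratory objective, repeated in Section 9.4.3.2, cannot be answered from Appendix 7. The perceived-ability part is not directly measured. Ease of use is covered.

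The consequence is minor: part of one descriptive exploratory endpoint is affected, in the inhaled arm only. The pharmacokinetic and safety objectives are untouched.

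The conclusion assumes that the form printed in Appendix 7 is the whole instrument, as Section 9.4.3.2 indicates, and that perceived ability means the respondent's view of her own ability.

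**What to change.** Add two items to Appendix 7, with the same four response options:

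- whether the instructions for using the inhaler were clear;
- whether she felt able to use the inhaler as she used it in the study.

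Leave the existing four items exactly as worded, so that answers before and after the change remain comparable. The ability item should be tied to what she actually did. Asking about loading or priming would seek an opinion on a step she did not perform.

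The cost is two tick-box items and the matching case report form fields, plus missing answers from women who have already completed. Section 2.2.2 reports that 10 Group 1 subjects had completed all procedures before the temporary halt. If they were split 5 and 5, as the interim review rule in Section 9.3.2.1 implies, about 5 had received the inhaler and would lack the new items. Section 9.3.2 provides for Group 1 to restart, so women dosed after the change could still be asked.

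If the form cannot be changed, remove the instructions and perceived ability from the objective in both the synopsis and Section 3.1, and remove the instructions from Section 9.4.3.2. All three places need the edit, or the synopsis and body will disagree. This costs only text changes, but it gives up the two constructs.
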